#### 7.3.2 Exposure/independent variables of interest

The survey does not evaluate outcomes related to exposure to a medicinal product. However, it does evaluate the effectiveness of the Piqray educational material, and therefore, the exposure of interest can be considered as the Piqray **Guide for HCPs**.

## 7.3.3 Other covariates/control variables

Covariates include HCP characteristics as shown in Table 7-2.

| Table 7-2 | Covariates collected in the survey |
|-----------|------------------------------------|
|-----------|------------------------------------|

| Original data collected   | Variable type | Operational definition/derivation  |
|---|---------------|--|
| Primary medical specialty   | Categorical   | Surgeon/surgical oncologist, radiation oncologist/radiologist, medical oncologist, other |
| Years working with oncology patients  | Categorical   | Less than 5 years, 5 to <10 years, 10 to <15 years, >15 years, prefer not to answer      |
| Number of patients for which
the HCP has prescribed
Piqray within the past 12
months | Categorical   | 1-5, 6-10, >10, don't know/am not sure   |
| Last time prescribed Piqray   | Categorical   | Less than 3 months ago, 3 to <6 months ago, don't know/am not sure                       |
| Investigator in a Piqray clinical trial   | Categorical   | Yes, No, don't know/am not sure  |

## 7.4 Data sources

A minimum sample of 30 to 50 HCPs from the included countries will be recruited from the target population of oncologists/HCPs who may prescribe Piqray and were on the lists for dissemination of the Piqray Prescriber's/HCP Guide for hyperglycemia. To endeavor to achieve

a larger sample than 30-50 completed surveys, recruitment will remain open until the end of the data collection period, and will not be closed early even if 50 completed surveys have been reached sooner. If after two reminders the target sample size has not been achieved, the sample may be supplemented through additional outreach based on internet research or outreach through applicable professional societies. Additionally, up to 2 additional countries may be included, depending on the timing and approval of commercialization of Piqray in additional EU/EEA countries relative to the survey study milestones and requirements (in each country, recruitment must take place a minimum of 6 months following the reimbursement and launch of Piqray, and must be open a minimum of 3 months before the end of data collection period).

Invitations to participate in the survey will be sent to approximately 1000 HCPs by either email (preferred) or by post mail (if email is not available) using the available contact information. The invitation letter will include information about the survey, a unique code, and instructions for accessing the survey. The unique code will be used to track who has already completed a survey so that reminders are only sent to HCPs who have not yet completed the survey.

All data for the survey will be collected by web-based data capture. The survey will be available for completion in English or native language spoken in participating countries depending on HCPs' preference.

The survey is anticipated to be open for a minimum of 3 months per country, measured from the date the survey is launched/initial invites sent in each country. Metrics will be tracked to monitor survey progress (e.g., number of eligible/ineligible HCPs, number of completed surveys). Follow-up reminders will be sent to non-respondents using the available contact information. Reminders will be sent within 2-4 weeks of the previous invite/reminder, and the maximum number of follow-up attempts per HCP will not exceed two. As an acknowledgement of their time and input, HCPs who complete the survey will receive fair market value (FMV) compensation if allowed, feasible, and in accordance with local regulations. The FMV compensation will be based on a survey that should take 15-20 minutes to complete.

## 7.5 Study size

Research has shown that response rate in HCP surveys can be expected to be rather low. A recent meta-analysis of data from 23 HCP surveys found the proportions of completers from invited participants ranging from 0.5% to 26.0% in each survey, with a pooled estimated proportion of 2.1% (95% confidence interval [CI]: 2.1 to 2.2) based on a fixed effects model, or 4.7% (95% CI: 3.0 to 6.6) based on a random effects model. For example, up to 10,000 eligible physicians must be contacted to obtain 200 completed questionnaires (Artime et al 2019).

It is estimated that response rates in the range of 4-5% are achievable; as a result, to approximately1000 potentially eligible physicians must be contacted to obtain 30 to 50 completed questionnaires based on the estimated response rate. Table 7-3 provides an estimate of the maximum number of Piqray prescribers in each of the potential participating countries. Up to 2 additional countries may be included in the survey depending on the timing and approval of commercialization of Piqray in additional EU/EEA countries relative to the survey study milestones and requirements.

|                 | Estimated maximum number of potential Figray prescribers |                        |  |  |  |  |  |
|-----------------|--|------------------------|--|--|--|--|--|
| Country         | # Potential prescribers                                  | Reimbursement status   |  |  |  |  |  |
| Austria         | 280  | Reimbursed             |  |  |  |  |  |
| Luxembourg      | 20   | Reimbursed             |  |  |  |  |  |
| Norway          | 175  | Pending review outcome |  |  |  |  |  |
| Slovenia        | 30   | Reimbursed             |  |  |  |  |  |
| Sweden          | 340  | Reimbursed             |  |  |  |  |  |
| The Netherlands | 100  | Reimbursed             |  |  |  |  |  |
| Total           | 945  |                        |  |  |  |  |  |

 Table 7-3
 Estimated maximum number of potential Piqray prescribers

The primary evaluation criteria (i.e., endpoints) are prescribers' knowledge of the risks of hyperglycemia with Piqray and practices recommended to minimize this risk, expressed as the weighted composite percentage of HCPs with correct responses to the key question set. The sample size is based on the primary endpoint.

Table 7-4 provides the precision and corresponding 2-sided 95% exact confidence intervals (CI) around expected levels of knowledge by various numbers of completed surveys for this study. With a targeted weighted composite knowledge level of  $\geq$ 70% for the primary endpoint, a sample size of 30 to 50 HCPs allows estimation of a minimum HCP knowledge level of at least 70% with a precision ranging between 13.4%-17.4%. To endeavor to achieve a larger sample than 30-50 completed surveys and improve precision of the knowledge level estimates, recruitment will remain open until the end of the data collection period, and will not be closed early even if 50 completed surveys have been reached sooner.

| Sample | Probable respondent knowledge levels |               |                   |               |                  |               |                  |               |                  |                           |  |
|--------|--------------------------------------|---------------|-------------------|---------------|------------------|---------------|------------------|---------------|------------------|---------------------------|--|
| size   | 50% 60%                              |               | 60%               | 6 70%         |                  | 80%           |                  |               | 90%              |                           |  |
|        | Precisi
on (%)                    | 95%
Cl     | Precisi
on (%) | 95%
CI     | Precision
(%) | 95%
CI     | Precision
(%) | 95%
CI     | Precision
(%) | 95%
Cl                 |  |
| 30     | 18.7                                 | 31.3-
68.7 | 18.4              | 40.6-
77.3 | 17.4             | 50.6-
85.3 | 15.5             | 61.4-
92.3 | 12.2             | 73.5 .
97.9 |  |
| 50     | 14.5                                 | 35.5-
64.5 | 14.2              | 45.2-
73.6 | 13.4             | 55.4-
82.1 | 11.9             | 66.3-
90.0 | 9.3              | 73.2
96.7              |  |
| 100    | 10.2                                 | 39.8-
60.2 | 10.0              | 49.7-
69.7 | 9.4              | 60.0-
78.8 | 8.3              | 70.8-
87.3 | 6.4              | 82.4
95.1              |  |
| 150    | 8.3                                  | 41.7-
58.3 | 8.1               | 51.7-
67.9 | 7.6              | 62.0-
77.2 | 6.7              | 72.7-
86.1 | 5.2              | 84.0
94.3              |  |
| 200    | 7.2                                  | 42.9-
57.1 | 7.0               | 52.9-
66.8 | 6.6              | 63.1-
76.3 | 5.8              | 73.8-
85.3 | 4.4              | 85.0-
93.8             |  |
| 300    | 5.8                                  | 44.2-
55.8 | 5.7               | 54.2-
65.6 | 5.4              | 64.5-
75.1 | 4.7              | 75.0-
84.4 | 3.6              | 86.0-
93.2             |  |

Table 7-4Precision and 95% confidence intervals for various combinations of
sample size and knowledge levels

Note: Calculated using PASS 13 software (Hintze 2014), exact confidence intervals for one proportion (Clopper-Pearson).

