#### Data sources

HCPs will be recruited from the target population of oncologists/HCPs who may prescribe Piqray, and were on the lists for dissemination of the Piqray Prescriber's/HCP Guide for hyperglycemia. If after two reminders the target sample size has not been achieved, the sample may be supplemented through additional outreach based on internet research or outreach through applicable professional societies.

Invitations to participate in the survey will be sent to at least 1000 HCPs by either email (preferred) or by post mail (if email is not available) using the available contact information.

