## 7.9 Limitations of the research methods

The primary limitation of a cross-sectional survey is selection bias due to use of a convenience sample and/or low response rates. A key requirement of this study is that it reflects a representative view across the HCPs who have prescribed Piqray. To minimize selection bias, HCPs will be recruited from a geographically representative sample of countries where Piqray is commercialized. Due to privacy laws, lists of actual prescribers of Piqray in these countries may not be available. Therefore, to promote generalizability, all potential prescribers in the participating countries (i.e., HCPs who were sent the Piqray educational material) will be invited to screen for participation in the survey. To further minimize selection bias:

- HCPs will receive up to 2 reminders to encourage their participation, and
- The eligibility criteria are limited to reflect the real-world EU/EEA population of HCPs prescribing Piqray.

There may be some recall bias associated with HCPs thinking back over time when answering the survey. To minimize this bias, respondents will be limited to those who have prescribed Piqray within the 6 months prior to completing the survey.

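### Section 7.5 ties 30 to 50 completes to about 1000 invitations at 4-5%, which gives 40 to 50; the abstract's floor of 1000 invitations exceeds the 945 prescribers in the six named countries

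*Protocol*

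**What the plan says.** Section 7.5 (Study size) reviews completion rates in surveys of healthcare professionals and settles on a planning value: "It is estimated that response rates in the range of 4-5% are achievable". From this it concludes that approximately 1000 "potentially eligible physicians must be contacted to obtain 30 to 50 completed questionnaires based on the estimated response rate".

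The number of invitations appears in two forms:

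- Abstract, Data sources: "Invitations to participate in the survey will be sent to at least 1000 HCPs".
- Section 7.4: "Invitations to participate in the survey will be sent to approximately 1000 HCPs".

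Table 7-3 in section 7.5 estimates the maximum number of potential prescribers in the six named countries at 945. Norway contributes 175 of these, with its reimbursement status given as "Pending review outcome".

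Section 7.9 says that all potential prescribers in the participating countries, meaning "HCPs who were sent the Piqray educational material) will be invited to screen for participation in the survey".

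Two routes could enlarge the pool. Section 7.5 says: "Up to 2 additional countries may be included in the survey depending on the timing and approval of commercialization of Piqray". Section 7.4 says that, if the target is missed after two reminders, "the sample may be supplemented through additional outreach based on internet research or outreach through applicable professional societies".

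For 30 to 50 completes and a knowledge level of 70%, section 7.5 states a precision between 13.4% and 17.4%.

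**The concern.** The text presents the 30 to 50 completes as following from the 4-5% rate, and the lower end does not follow. A reader cannot tell whether the sponsor is planning on a 3% response or on fewer than 1000 invitations.

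Separately, the abstract's floor of 1000 invitations is larger than the estimated maximum for the six named countries, all of whose listed prescribers are already to be invited. The floor therefore depends on additions that the protocol describes only as possible.

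These figures are the protocol's main statement of feasibility; item 12.2 of the ENCePP checklist in Annex 2 points to section 7.5 for it. At stake is whether the number of completes and the best-case precision rest on a consistent set of inputs.

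**Working it through.** **Inputs.** Response rate 4-5%, about 1000 contacts and 30 to 50 completes (section 7.5). Prescribers by country (Table 7-3): Austria 280, Luxembourg 20, Norway 175, Slovenia 30, Sweden 340, the Netherlands 100. Knowledge level 70% with two-sided 95% exact (Clopper-Pearson) intervals (Table 7-4).

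**1. The plan's own figure.** Completes = invitations × response rate.

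- 1000 × 0.05 = 50. The upper end reproduces.
- 1000 × 0.04 = 40. The lower end of 30 does not reproduce.
- 30 / 1000 = 3%, which is below the stated range. It equals the lower limit of the cited random-effects interval (3.0 to 6.6), but section 7.5 does not give that as its basis.
- Inverse check: 30 / 0.04 = 750 invitations and 50 / 0.05 = 1000. No single number of invitations gives both 30 and 50 at 4-5%.

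**2. The pool.** 280 + 20 + 175 + 30 + 340 + 100 = 945, so the total in Table 7-3 is right. It is 1000 − 945 = 55 short of 1000 (5.5%). Without Norway it is 945 − 175 = 770, which is 230 short (23%).

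**3. Expected yield from the named countries, with precision.** The half-width is half the length of the Clopper-Pearson interval at 70%. As a check on method, n = 30 gives 17.3 and n = 50 gives 13.4 points, against 17.4 and 13.4 in Table 7-4, so the stated precision figures reproduce to within rounding.

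| Invited | Rate | Completes | Half-width at 70% (points) |
|---|---|---|---|
| 1000 | 4% | 40 | 15.0 |
| 1000 | 5% | 50 | 13.4 |
| 945 | 4% | 37.8, about 38 | 15.4 |
| 945 | 5% | 47.25, about 47 | 13.8 |
| 770 | 4% | 30.8, about 31 | 17.0 |
| 770 | 5% | 38.5, rounded up to 39 | 15.2 |

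**4. Rates needed for the two ends of the range.**

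- For 50 completes: 50 / 945 = 5.3% and 50 / 770 = 6.5%, both above 4-5%.
- For 30 completes: 30 / 945 = 3.2% and 30 / 770 = 3.9%, both below 4%.

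**The case against.** The strongest reply is that the slip is conservative. The yields at 4-5% are 40-50 from 1000, 38-47 from 945 and 31-39 from 770. All lie inside 30-50, and their half-widths lie inside the stated 13.4% to 17.4%. No precision figure in section 7.5 or Table 7-4 is made wrong by this. That stands, and it limits the point to how the range is derived and how the invitation count is stated.

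A reader might infer that 1000 invitations cannot be delivered. The documents do not support that. The 945 covers the six named countries only; up to two more may be added, and outreach beyond the lists is allowed if the target is missed. The body's approximate 1000 can also reasonably cover 945. What remains is that the abstract's floor is unconditional while both routes to it are contingent, and that no prescriber count is given for any added country.

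A reader might also infer that any response below 4% takes the study under 30 completes, the smallest size in Table 7-4. That is nearly true for 770 invitations, where the threshold is 3.9%. With 945 the threshold is 3.2%.

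Finally, one might press the lower cited rates, such as the fixed-effect 2.1%. The protocol discloses them and adopts 4-5%, close to the random-effects estimate of 4.7%. Whether that is optimistic is a matter of judgement, and the arithmetic does not show it to be wrong.

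**Conclusion.** The point holds in a limited form. The lower end of 30 completes does not follow from 4-5% of about 1000; it implies 3%. The abstract's floor of 1000 invitations disagrees with section 7.4 and exceeds the Table 7-3 maximum by 55, or by 230 if Norway is not included, unless countries or outreach are added.

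The practical effect is small. From the named countries the best case at the assumed rates is about 47 completes instead of 50, which moves the best half-width from 13.4 to 13.8 points (15.2 without Norway). The stated ranges for completes and precision still contain every yield computed at 4-5%.

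This rests on three assumptions: the Table 7-3 counts are the numbers invited, all six countries (or all but Norway) take part, and no off-list outreach is used. The protocol allows as few as four countries, so the number invited could also be smaller than either figure used here.

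**What to change.** In section 7.5, do one of two things:

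- state the response range as 3-5%, which matches 30 to 50 completes from about 1000 contacts; or
- keep 4-5% and state the expected completes as 38-47 from 945 invitations and 31-39 from 770, with half-widths of 15.4 to 13.8 and 17.0 to 15.2 points at 70%.

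In the abstract, replace the floor of 1000 with wording that agrees with section 7.4 and Table 7-3: invitations go to every HCP on the dissemination lists of the participating countries, up to 945 in the six named countries, and to more only if countries or outreach are added. The 945 should not be written as a cap on the whole study, because that would conflict with the four-to-eight-country design and the outreach provision.

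The cost is a change of wording and, under the second option, a slightly less favourable best-case precision. Recruitment does not change.

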## 7.6 Data management

Survey data collection will be completed on-line in Confirmit, a software platform specifically designed for the creation and delivery of multi-lingual surveys. Data collected will be stored at secure servers and will be maintained to ensure compliance with applicable local and national regulations.

Response sets for multiple-choice questions will be randomised to minimize bias. To minimize likelihood that respondents would look up answers and/or discuss the survey while taking it, respondents will be asked to complete survey in one sitting and will not be allowed to revise their answers after they advance to the next question.

Survey database lock is anticipated to occur shortly after the survey is closed in the last country. To reduce opportunity for bias, survey respondents will not be contacted to clarify or revise their responses to knowledge assessment-related questions.

Data management will be in accordance with the standard operating procedures (SOPs).

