#### 7.3.1 **Outcomes/endpoint variables**

Primary endpoint:

- Levels of knowledge of the risk for hyperglycemia, and risk factors for hyperglycemia, (survey question 4A, 6),
- Levels of knowledge of signs and symptoms of hyperglycemia (survey questions 5A-C), •
- Levels of knowledge of recommendations for monitoring for hyperglycemia prior to, and during, treatment with Pigray (survey questions 8A-C, 10, 15) and
- Levels of knowledge of recommendations for managing hyperglycemia during treatment ٠ with Piqray (survey questions 12-14).

The primary endpoint is a composite endpoint that combines correct responses given by HCPs to questions included in the composite. Specifically, the primary endpoint is a weighted composite knowledge score aggregated across the following survey questions: 4A, 5A-C, 6, 8A-C. 10, and 12-15. It is calculated as the number of all correctly answered questions divided by the number of all answered questions (i.e. questions that were answered either correct and not correct – unanswered questions are excluded).

Success criteria on the primary endpoint is defined as a weighted composite knowledge level of at least 70% across these key questions.

Secondary endpoint questions:

- Levels of reported receipt and reading of the Pigray Prescriber's/HCP Guide for • hyperglycemia, assessed as the percentages of HCPs who report receipt and reading of the same (survey questions 1, 2)
- HCPs' knowledge levels for each survey question regarding knowledge of, and • management of, hyperglycemia, assessed as the percentages of HCPs with correct responses to each question (individual responses to survey questions 4-15)
- The distribution of responses regarding the primary source from which HCPs learned • about the messages included in the Piqray Prescriber's/HCP Guide for Hyperglycemia, assessed as the percentages of HCPs who report using each of the possible sources as the primary source they used (survey question 3).

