#### [END SURVEY SCREENING QUESTIONS]

#### MAIN SURVEY

[Preamble 1]: These questions are about important product information for Piqray. Please be sure to review all response choices for each question before answering each question.

1. Did you receive the "Piqray Prescriber's/HCP **Guide for Hyperglycemia**" that reminds healthcare professionals about certain how to identify, and manage, hyperglycemia in patients treated with Piqray?

```
🗆 Yes
```

#### □ No → PROCEED TO QUESTION 3

- □ I don't know/am not sure → PROCEED TO QUESTION 3
- 2. Did you read or review the "Piqray Prescriber's/HCP Guide for Hyperglycemia"?
  - Yes, all of it
    Yes, some of it
    No
    I don't know/am not sure
- What is the primary source you use to learn about the indication, precautions for use, and potential risks for Piqray? (please tick only 1 response)

D Piqray Summary of Product Characteristics

- D Piqray Prescriber's/HCP Guide for Hyperglycemia
- National Competent Authority website
- Professional Society or Congress
- □ The Piqray product website
- The European Medicines Agency website
- Clinical practice guidelines
- A representative from Novartis
- □ Other (not listed above)
- □ I do not know/am not sure

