#### [ON-LINE SURVEY - PROGRAMMER: RANDOMISE THE ORDER OF THE FIRST 4 RESPONSE OPTIONS]

7. According to the Piqray Prescriber's/HCP Guide for Hyperglycemia and SmPC for Piqray, please indicate if the following statement is True or False: For patients at higher risk for developing hyperglycemia, there is no need to consult with a healthcare professional or endocrinologist experienced in the treatment of hyperglycemia.

🗆 True

✓ False

□ I don't know/am not sure

8. According to the Piqray Prescriber's/HCP Guide for Hyperglycemia and SmPC for Piqray, to mitigate risk of hyperglycemia, which of the following should be performed before a patient starts treatment with Piqray?

|   |  | Check the box if
the action should
be performed |
|---|--|---|
| Α | Obtain a fasting glucose and
HbA1c  | 1   |
| В | Optimize the patient's level of
blood glucose, as applicable                      | 1   |
| с | Counsel the patient about the risk of hyperglycemia                                  | 1   |
| D | Increase the dose of their current
antihyperglycemic medication, if
applicable |   |
| E | Consult with a diabetologist for
all patients, even if they are not
diabetic   |   |
| F | I don't know/am not sure   |   |

[ON-LINE SURVEY - PROGRAMMER: RANDOMIZE THE ORDER OF THESE 5 QUESTIONS]  According to the Piqray Prescriber's/HCP Guide for Hyperglycemia and SmPC for Piqray, please indicate if the following statement is True or False: The monitoring schedule of fasting glucose levels for patients receiving Piqray is the same for patients with, and without, risk factors for hyperglycemia.

D True

✓ False

□ I don't know/am not sure

10. According to the Piqray Prescriber's/HCP Guide for Hyperglycemia and SmPC for Piqray, at what frequency should fasting glucose testing be performed for all patients treated with Piqray?

□ Weekly for the first 3 months of treatment, then monthly thereafter

✓ At weeks 1, 2, 4, 6, and 8 after treatment start, then monthly thereafter □ Daily for the first 2 weeks of treatment, then at Weeks 4, 6, and 8, then monthly thereafter

□ I don't know/am not sure

[ON-LINE SURVEY - PROGRAMMER: RANDOMIZE THE ORDER OF THE FIRST 3 RESPONSE OPTIONS]

11. According to the Piqray Prescriber's/HCP Guide for Hyperglycemia and SmPC for Piqray, at what frequency should HbA1c testing be performed for all patients treated with Piqray?

Monthly for the first 3 months of treatment, then quarterly thereafter

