 4 weeks after treatment start, then every 3 months thereafter
 Monthly for the first 6 months of treatment, then annually thereafter
 I don't know/am not sure

[ON-LINE SURVEY - PROGRAMMER: RANDOMIZE THE ORDER OF THE FIRST 3 RESPONSE OPTIONS]

 According to the Piqray Prescriber's/HCP Guide for Hyperglycemia and SmPC for Piqray, please indicate if the following statement is True or False: For fasting glucose values that are ≤250 mg/dL (≤13.9 mmol/L), no Piqray dose adjustment is required. It is recommended to manage by initiating or intensifying oral antihyperglycemic treatment.

🖌 True

🗆 False

□ I don't know/am not sure

- 13. According to the Piqray Prescriber's/HCP Guide for Hyperglycemia and SmPC for Piqray, which of the following fasting glucose values (blood) that are elevated (above the upper limit of normal) require Piqray dosing to be interrupted?
  - Any fasting glucose value >160 mg/dL (>8.9 mmol/L)
  - □ Any fasting glucose value >200 mg/dL (>27.8 mmol/L

□ Any fasting glucose value >200 mg/dL (>27.8 mmol/L

Any fasting glucose value >250 mg/dL (>13.9 mmol/L)

□ I don't know/am not sure

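### The measures against looking up answers do not act while a question is on screen, 8 of the 13 composite items name the documents that hold the answer, and nothing collected would show whether they were consulted

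*Protocol*

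**What the plan says.** Section 7.6 recognises look-up as a threat. It introduces its two measures with the words "To minimize likelihood that respondents would look up answers and/or discuss the survey while taking it" and then states that "respondents will be asked to complete survey in one sitting and will not be allowed to revise their answers after they advance to the next" item.

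The primary endpoint in section 7.3.1 is a composite "aggregated across the following survey questions: 4A, 5A-C, 6, 8A-C. 10, and 12-15". It is the number of correct answers divided by the number of answered questions, and success is a value of at least 70%. Section 7.7.2 compares the point estimate with that threshold.

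In Appendix 13.1, Q7 to Q15 all open with the same reference to the two source documents. Examples are Q8 ("According to the Piqray Prescriber's/HCP Guide for Hyperglycemia and SmPC for Piqray, to mitigate risk of hyperglycemia"), Q10 ("According to the Piqray Prescriber's/HCP Guide for Hyperglycemia and SmPC for Piqray, at what frequency should fasting glucose testing be performed"), and Q12 and Q14 ("According to the Piqray Prescriber's/HCP Guide for Hyperglycemia and SmPC for Piqray, please indicate if the following statement is True or False"). Q4, Q5 and Q6 have no such opening.

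The instruction at the head of the main survey, Preamble 1, concerns reading the options: "Please be sure to review all response choices for each question before answering each question". Q16 to Q20 ask about specialty, experience, recent prescribing and trial involvement, and the questionnaire then closes. On timing, section 7.4 gives only an expected duration for compensation: "The FMV compensation will be based on a survey that should take 15-20 minutes to complete". No time limit is stated.

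The limitations in section 7.9 are selection bias and recall bias.

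**The concern.** The primary objective is what prescribers know. An answer read from the Guide during the survey shows that the Guide can be found, not that its content is known. Such answers are mostly correct, so the error runs one way, towards success, and a point-estimate criterion has no margin to absorb it.

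The items exposed are every monitoring and management item in the composite, which are the ones closest to what the educational material is meant to change.

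This cannot be left to the analysis plan. The questionnaire is fixed in the protocol's appendix, and no later analysis can recover whether sources were consulted if the question was never asked.

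**Working it through.** **The plan's own figure.** The only sample-size figure is the precision at 70% knowledge in section 7.5. Exact (Clopper-Pearson) limits reproduce it:
- n = 30, 21 correct: 50.6 to 85.3, half-width (85.3 − 50.6)/2 = 17.35, printed as 17.4.
- n = 50, 35 correct: 55.4 to 82.1, half-width (82.1 − 55.4)/2 = 13.35, printed as 13.4 (13.37 before the limits are rounded).

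The present point does not depend on it. These half-widths describe sampling error and contain no allowance for look-up.

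**What the two controls act on.**
- The block on revision applies after the respondent has advanced. A look-up made before answering is complete by then.
- The single sitting is a request. A self-administered web survey with no stated time limit lets a document be opened alongside the question.

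**Item count** (list from section 7.3.1, stems from Appendix 13.1).
- All composite items: 4A (1), 5A-C (3), 6 (1), 8A-C (3), 10 (1), 12-15 (4). Total 13.
- Items whose stem names the Guide and SmPC: 8A-C (3), 10 (1), 12-15 (4). Total 8.
- Share: 8/13 = 61.5%.
- Table 7-1 and the appendix also mark 5F, 5G and 5H as key. With those, the share is 8/16 = 50%.

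**Size, as an illustration.** The protocol gives no look-up rate and no expected knowledge by item. Assume that every item is answered and counts equally, that true knowledge on the 8 items is 55%, and that a respondent who looks up gets all 8 right. With r the share of respondents who look up:

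rise = r × 8 × (1 − 0.55) / 13

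| r | Rise, 13 items | True composite for which the verdict changes | Rise, 16 items |
|---|---|---|---|
| 10% | 0.10 × 3.6/13 = 2.8 points | 67.2% to just under 70% | 2.25 points |
| 20% | 0.20 × 3.6/13 = 5.5 points | 64.5% to just under 70% | 4.5 points |
| 30% | 0.30 × 3.6/13 = 8.3 points | 61.7% to just under 70% | 6.75 points |

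Worked case: add the assumption of 81% true knowledge on the other 5 items. The true composite is (5 × 0.81 + 8 × 0.55)/13 = 65.0%. It shows as 67.8% at r = 10% (still a fail), 70.5% at 20% and 73.3% at 30%. The crossing point is 5.0/27.7, or about 18% of respondents.

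**A second parameterisation.** Let p be unaided knowledge, the same on all items, and f the share of otherwise wrong or unsure answers on the 8 items that look-up corrects:

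observed = p + (8/13) × f × (1 − p)

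- The p that shows as 70% is 68.0%, 64.5% or 56.7% for f = 10%, 25% or 50%.
- At p = 60%, f must reach 0.10/(0.615 × 0.40), about 41%, before the composite shows 70%. On 16 items it is 50%.

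Both forms agree on direction. They also show that the shift is decisive only when true knowledge is fairly close to the threshold.

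**The case against.** Four stronger readings are tempting, and the document does not support them.

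- *That section 7.6 promises something it fails to deliver.* It claims only to make look-up less likely. Discouraging breaks and blocking return to earlier answers plausibly does some of that, and some look-up is inherent in any unsupervised web survey. This is a limited control with an unlisted residual risk, not a contradiction.
- *That respondents are never told to answer unaided.* This cannot be asserted. The survey introduction, the screening pages and the invitation letter are not in the text at hand. The one-sitting request from section 7.6 does not appear in the visible questionnaire either, so the respondent instructions shown are incomplete.
- *That the stems invite an open-book answer.* That is a judgement. Q3 lists other sources of information, such as clinical practice guidelines, so the stem may be there to fix the standard against which an answer is marked. It still points to the documents that contain the answer.
- *That look-up would turn a fail into a pass.* That depends on the inputs chosen. In the worked case, 10% look-up still fails.

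It can also be said that a self-reported item has limited yield in a planned sample of 30 to 50. The ENCePP checklist itself says that small numbers limit sensitivity analyses. That stands as a limit on what the remedy can show. It does not remove the reason to collect the item.

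**Conclusion.** The point holds as a cheap improvement to make before data collection, not as an error that invalidates the design. The stated controls do not reach a look-up made before answering. Of the composite items in section 7.3.1, 8 of 13 (8 of 16 with 5F-H) name the source documents. The visible questionnaire collects nothing that would separate open-book answers, and section 7.9 is silent on look-up. Any resulting bias would run upward and could not be detected.

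Its size cannot be derived from the protocol. The range of 2.8 to 8.3 points rests on an assumed 55% true knowledge, 10-30% look-up and perfect scores after look-up. A shift of that size alters the conclusion only if the true composite lies within the same distance below 70%.

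**What to change.** - Add one closing item after Q20: 'Did you consult any source while answering Q4-Q15?' (yes/no).
- Report the primary composite also without those who answer yes, and state whether the 70% conclusion is the same in both.
- Name look-up as a limitation in section 7.9.
- Confirm that the survey introduction asks for answers without consulting the Guide, the SmPC or other sources. If it does not, add that sentence to Preamble 1.

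The stems can stay if they are meant to set the reference standard.

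The cost is one questionnaire item, one table row and one or two sentences. The downside is that self-reported look-up will be under-reported and the subset will be smaller and less precise. Agreement between the two composites would therefore not prove absence of bias, whereas a clear difference would be informative.
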